3. STUDY PARTICIPANTS

Study participants in this project include participants recruited for cervical cancer CHW-led educational workshops led by MCHH. Participants can be either Hmong, Karen, Burmese or Karen speaking and are recruited by MCHH with a particular focus on those who are behind or have never had cervical cancer screening. The main objective is to provide education to these participants on cervical cancer prevention and screening with subsequent invitation for immediate post-workshop sample collection for cervical cancer screening.

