13. PROCEDURES INVOLVED

13.1 Project Activities

13.1.1 Pre-Participation Intake

Intake will be done upon recruitment, after informed consent is obtained and prior to start the assigned workshop. Forms to be used are the standard intake forms used by MCHH for previous workshop participations and gathers information such as demographics, primary care physician (PCP), and insurance coverage (full intake form in Appendix A). Intake forms are assigned an ID # which will be used to extract data for this research program. [name] (MCHH Director) will maintain original intake forms at the MCHH community center and participant identities to the study ID separately from other data. Following information from the intake form will be collected for this research program:

- ID Number
- First and last initials
- Workshop Date
- Ethnicity
- Date of Birth
- Gender
- Month and year of previous Pap Test
- Type of Insurance
- Answer to the following question “What reasons may be stopping you from getting a Pap Test?” (options below)

 No symptoms	 I don't want to know the results
 No transportation	 Childcare
 Too expensive/No insurance	 No family history of cervical cancer
 I don't know where to go	 My doctor never mentioned it
 Spouse will not allow it	 Embarrassed
 I'm too busy/No time	 Long wait to get an appointment
 I am afraid it will hurt	 None

If a participant has a PCP, MCHH can fax or mail the results of their screening tests directly to their PCP. For participants who do not have a PCP and would like to establish with one, a list of available providers in the area accepting new patients will be obtained prior to the start of the research study.

Providers accepting new patients will be oriented by phone by a research team member prior to the start of the study. They will be provided with a brief overview of the research study and purpose. In addition, when receiving participant results on cervical cancer screening, cover letter will include a brief overview of the research project, purpose, recommend follow-up, and need for patient to establish as a new patient to their clinic.

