16.2 Data Storage and Maintenance

Data will be stored in compliance with HIPAA regulations on encrypted UW research servers in the Department of Family Medicine and Community Health. All records including study enrollment information will be housed in compliance with regulations indefinitely until the analysis is complete. The process of destroying of these records post-analysis will comply with applicable UW or policies for research records.

The study ID, date of workshop attendance, age, zipcode, type of screening done, and screening results will be stored in REDCap Institute for Clinical and Translational Research (ICTR). Portable devices will be used to access secure web-based application of ICTR's RedCap. No data will be stored locally on the device. Only encrypted devices will be used.

Research Electronic Data Capture (REDCap) is a largely self-service, secure, web-based application for building and managing data collection forms. REDCap provides data management functionality by allowing the development of instrument and surveys to support data capture for research studies.

Post-workshop survey results will be stored in Qualtrics and not linked to study ID, results will be entirely anonymous. Paper copies of the intake form will be stored in a locked location at the Milwaukee Consortium for Hmong Health.

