20.2 Sample Size Justification

For this pilot study, we will enroll 250 participants, which is based on the feasibility of the number of workshops possible during the program length, funding, and resources available through MCHH.⁹ Power estimates are based on comparing the rate of participation between the intervention arm (participants offered self-collected hrHPV) and the control arm (participants offered clinician-collected screening). Estimates of screening rates for the Hmong women population (percent that have had a clinician-collected screening in the last 2-3 years) range from 61- 81%. As we do not have estimates for rates for Karen, Karen, Burmese, or Hmong women, we will use these estimates for participation rates in the control arm. The table below shows the detectable participation rates (and differences between proportions) for the intervention arm for different combinations of power (1- β) and values for the control arm from 0.61-0.81, for the hypotheses $H_0: P \leq p_0$ vs. $H_1: P > p_0$, where p_0 is the rate of participation in the control arm, for a sample size of 250 (125/arm), with a one-sided level 0.05 binomial test.

Control Participation Rate	Detectable Participation Rate (Difference)		
	0.80	0.85	0.90
0.61	0.77 (0.16)	0.78 (0.17)	0.79 (0.18)
0.71	0.85 (0.14)	0.86 (0.15)	0.87 (0.16)
0.81	0.93 (0.12)	0.93 (0.12)	0.94 (0.13)

As an example, if there is a participation rate of 0.81 for those offered clinician-collected screening, we will be able to detect a rate of 0.93 (a difference of 0.12) in the participants offered self-collected hrHPV with a one-sided level 0.05 binomial test with a power of 0.85.

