20.3 Statistical Methods

20.3.1 Primary Outcome Measures and Analysis:

The primary outcome measure is uptake of cervical cancer screening. The results will be reported through summary statistics of the number of participants in each group subsequently engaging or seeking out cervical cancer screening either through services offered after workshop education or self-reported desire to follow up through their community health care provider. Comparisons between the study arms will be based on a binomial test. The analysis will indicate if participants offered additional self-collection education would be more willing to engage in cervical cancer screening. Summary statistics will also include uptake of screening differentiated by reported ethnicity.

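### The primary comparison makes no use of the screening history recorded at intake; adjusting same-day on-site uptake for it is a cheap gain in precision of unknown, probably modest, size

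*Combined protocol and SAP*

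**What the plan says.** Section 20.3.1 gives the primary analysis in one sentence: "Comparisons between the study arms will be based on a binomial test". Ethnicity enters only as a descriptive breakdown. Section 20.2 sizes the trial on the same unadjusted comparison, "for a sample size of 250 (125/arm), with a one-sided level 0.05 binomial test".

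Section 13.1.1 places intake after consent and before the workshop, and lists "Month and year of previous Pap Test" among the items taken for research under the ID number. The form in Appendix A also offers Never and Unknown. Section 3 says recruitment proceeds "with a particular focus on those who are behind or have never had cervical cancer screening", but Section 5 does not require a woman to be due for screening.

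Under Section 11, whole workshops are randomised, 15 per arm with 8 women each. Women choose their date without knowing its arm. No stratification or matching on screening history is described.

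Section 16.2 says "The study ID, date of workshop attendance, age, zipcode, type of screening done, and screening results will be stored in REDCap". The last Pap date is not in that list. The same section, with Section 13.1.3.2, keeps the post-workshop survey unlinked to study ID. Section 20.3.1 counts as uptake either screening offered after the workshop or a self-reported wish to be screened elsewhere.

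**The concern.** A woman's past screening behaviour is a natural candidate to predict whether she accepts screening that day. The protocol reasons this way itself: lacking participation data, it takes past screening rates of 61–81% and says "we will use these estimates for participation rates in the control arm". The value is measured before the workshop, so it is a true baseline covariate.

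With only 30 randomised groups, the share of never-screened or overdue women can differ between arms by chance. An unadjusted difference carries that imbalance and leaves the variation explained by history in the error term. Sample size is set by feasibility, so the analysis is one of the few places left to gain precision. Naming the covariate in advance also prevents a post-hoc choice if an imbalance appears.

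**Working it through.** **The plan's own figure.** Section 20.2 states that "if there is a participation rate of 0.81 for those offered clinician-collected screening, we will be able to detect a rate of 0.93" with power 0.85. An exact one-sided 0.05 Fisher test with 125 per arm gives 0.854. Its detectable rates, rounded up to two decimals, match all nine table cells. The plan's arithmetic is sound for independent women and no covariate.

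**Assumptions.** The documents give no history–uptake association, so ranges are used: share previously screened 0.3–0.7, odds ratio for uptake 2–10, and correlation of history within workshop (ICC) 0–0.2.

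**Chance imbalance.** For 15 v 15 workshops of 8 (120 per arm), with q the share previously screened:

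SD = √[2q(1−q)/120 × (1 + 7 × ICC)]

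- q = 0.3, ICC 0: √(0.42/120) = 0.059.
- q = 0.5, ICC 0.2: √(0.5/120 × 2.4) = 0.100.
- Across the range, the chance of an imbalance above 10 points is 9–32%.

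Shift in the arm difference = uptake gap × imbalance. At one SD with q = 0.5:

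- Gap 0.20, ICC 0: 0.20 × 0.0645 = 0.013.
- Gap 0.40, ICC 0.1 (design effect 1.7): 0.40 × 0.0842 = 0.034.

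At 1.96 SD, over ICC 0–0.2, the shift is 2.3–3.9 points for a 20-point gap and 4.6–7.8 for a 40-point gap. The planned detectable differences are 12–18 points.

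**Precision, treating women as independent.** The unadjusted variance is [p₀(1−p₀) + p₁(1−p₁)]/125. The adjusted variance averages the within-history-group variances and adds q(1−q)(d₁−d₀)²/250, where d is the arm difference in each history group. Example: 0.81 v 0.93, q = 0.5, odds ratio 5.

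- Group rates: control 0.699 and 0.921, intervention 0.885 and 0.975.
- Unadjusted sum: 0.1539 + 0.0651 = 0.2190.
- Adjusted sum: 0.1416 + 0.0631 + 0.25 × (0.054 − 0.186)²/2 = 0.2069.
- Variance ratio: 0.2069/0.2190 = 0.945.
- Power: Φ(0.12/√(0.2190/125) − 1.645) = 0.889 before, and 0.904 after.

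Over the three planned pairs (0.61/0.77, 0.71/0.85, 0.81/0.93):

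| Odds ratio | Gain in effective sample size | Gain in power (points) |
|---|---|---|
| 2 | 1–3% | under 1 |
| 3 | 2–6% | about 0.5–1.7 |
| 5 | 3–14% | about 1–3.5 |
| 10 | 5–29% | about 1–6.4 |

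**Precision at workshop level.** Simulation of 15 v 15 workshops of 8, uptake 0.61 v 0.77, half the women never screened or overdue, history ICC 0.1, and the same gap in both arms. Uptake is adjusted for history and workshop mean residuals are compared. History is the only source of workshop clustering here.

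| Gap (points) | Implied odds ratio, control / intervention | Variance ratio | Power |
|---|---|---|---|
| 20 | 2.4 / 3.3 | 0.91 | 0.83 → 0.86 |
| 30 | 3.7 / 7.0 | 0.83 | 0.83 → 0.88 |
| 40 | 6.1 / 24.4 | 0.71 | 0.79 → 0.90 |

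The last odds ratio is (0.97/0.03)/(0.57/0.43) = 24.4. With history unrelated to workshop (ICC 0), the ratios are 0.94, 0.89 and 0.80. One-sided error stayed near 0.05.

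**Less favourable inputs, same layout.**

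- Gap of 20 points in control and none in intervention: variance falls 1–3%, power stays at 0.84.
- Gaps of 20 and 10 points with 70% under-screened: variance falls 2–4%, power rises about 1 point.
- Gap of 10 points in both arms, ICC 0.1: variance falls 2%, power rises 0.2 points.

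**The case against.** An unadjusted randomised comparison is legitimate, especially in a pilot sized on feasibility, and the gain may be negligible. That stands. Section 1.1 presents self-collection as a way to reach under-screened women, so the gap may shrink in the intervention arm, and the gain shrinks with it. The direction is not certain either: women who are up to date may decline because they are not due.

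A reader might infer four stronger things that the documents do not support.

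- **That history is a leading driver of uptake.** No figure in the documents shows this. Using past screening rates as a stand-in for participation makes it plausible, no more.
- **That self-selected dates make the comparison biased.** Women do not know a workshop's arm when they choose, so an imbalance is random error. A test valid for the design covers it: with history ICC 0.1, an unadjusted workshop-level test held one-sided error at 0.050–0.052.
- **That the last Pap date will be unavailable for analysis.** Section 16.2 lists what REDCap holds and does not call it the analysis file. Ethnicity is also missing from that list, yet Section 20.3.1 plans results by ethnicity.
- **That one covariate repairs the whole primary outcome.** The stated-intention part comes from the anonymous survey (Appendix C, Sections C and G) and cannot be joined to a woman's history. Same-day screening is held by study ID, and it is the comparison described in Sections 2 and 8.

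Clustering is the larger problem. At an assumed outcome ICC of 0.05 (design effect 1 + 7 × 0.05 = 1.35), the planned test's nominal 0.05 becomes about 0.078. Adjusting for history within the planned binomial framework would not cure that.

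**Conclusion.** The point holds as a low-cost improvement, not as a flaw that invalidates the comparison. The plan collects a plausible baseline predictor, does not balance on it, and does not use it in the analysis. The gain is about 0–3 power points for weak to moderate associations. It reaches about 6–10 points only for very strong ones, such as an odds ratio of 10 or a 40-point gap in both arms. A one-SD imbalance shifts the estimate by about 1.3–3.4 points for gaps of 20–40 points.

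All of these sizes rest on assumed associations, shares and ICCs. The workshop-level figures also assume that the analysis already respects workshop randomisation, which the planned test does not. Extra workshop variation unrelated to history would make the proportional gain smaller.

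**What to change.** - **Section 20.3.1.** Prespecify intake screening history (never / overdue / up to date / unknown) as a covariate in a workshop-level primary analysis of same-day on-site screening. One way is to regress uptake on history without arm, average the residuals per workshop, and compare the 15 and 15 means. Report the adjusted difference with its 95% CI beside the unadjusted one. Categories are safer than a linear time term because the relation may not be monotone.
- **Definition of overdue.** Fix the analysis cut-off in advance. Section 14 cites both a three-year and a five-year interval, and the form asks only about Pap tests.
- **Section 16.2.** Carry last-Pap status into the analysis dataset under study ID, for example as a REDCap field.
- **Stated intention.** Say that it cannot be adjusted while surveys stay anonymous, and report it separately and unadjusted.
- **Age.** Optional; no gain from it has been shown.

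The cost is analysis wording, one field already on the intake form, and an explicit separation of on-site screening from stated intention in the primary outcome. No new data, visits or participants are needed. Adjusting the intention component as well would require linking the surveys, which is a larger change to the confidentiality provisions.

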20.3.2 Secondary Outcome Measures and Analysis

Qualitative survey data will be obtained through pre- and post-workshop surveys to evaluate the impact of the educational workshops.

Further statistical support for this program will be obtained through consultation with statisticians in the UW-Madison SMPH and/or UW Carbone Cancer Center Biostatistics Shared Resource. For quantitative data, differences will be tested with Wilcoxon Rank-Sum tests for continuous or ordinal categorical data, Chi-Squared tests for unordered categorical data, and binomial tests for dichotomous data.

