11. STUDY INTERVENTION

This randomized controlled trial will be done in partnership with MCHH. Previous partnership with MCHH and UW-Madison researchers developed cervical cancer educational workshops designed by CHWs to provide innovative mixed-modality education consisting of pictographs, flipcharts, videos, and hands-on models. These workshops to be conducted in Hmong, Karen, and Burmese and Karen languages were tested in mock workshops with Hmong and Karen participants and through a community advisory panel prior to dissemination. This approach caters to the unique culture and communication styles of Southeast Asian immigrant and refugee populations.

All workshops will be conducted by the CHWs on the study team. If the CHW is not fluent in the target language (such as Karen or Burmese), then the CHW will conduct all study activities in English with a translator available to translate all activities.

All participants attending a workshop will be randomized as a group to either a control or intervention group. Workshops in the control group will provide education recommending standard of care (clinician-collected hrHPV testing and cytology screening). Workshops in the intervention group will be offered the same education with additional education on the option of self-collection (HPV testing only) for their screening method. All participants will have the same basic demographic information collected in MCHH's standard intake form with an additional question on current barriers to screening.

Participants will self-select which workshop day they would like to attend depending on their preferred language. Participants can attend any available date a workshop is being offered until filled. Participants will be blinded to knowing which workshops are control or intervention groups. Participants during consent will be made aware there are two different groups and the difference between the intervention and control group is the education provided and screening method offered at the end of the education session. Participants will be provided the full study details at the end of their participation.

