13.1.3.2 UW Health Post-Workshop Satisfaction Survey (UW-PSS)

Additional survey questions will be administered verbally by CHWs and answers recorded in Qualtrics for data collection. Responses will not be linked to the study ID or other identifiable information. Theme of survey questions is below (full survey in Appendix C):

- Comfort with method (either self-collection or clinician-collection)
- How likely would the participant get screening for cervical cancer again?
- If self-collection (or clinician-collection) was an option, would they have preferred this method.

- If not getting screening today, will they go for screening in the near future?
 - o If not why? Where?
- Understanding of instructions (self-collection)

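### Section 20.3.2 promises a pre/post evaluation of the workshops, but no item is asked both before and after, and the stored survey answers carry no study ID, workshop session or ethnicity

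*Combined protocol and SAP*

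**What the plan says.** Section 20.3.2 sets the aim of the survey analysis: "Qualitative survey data will be obtained through pre- and post-workshop surveys to evaluate the impact of the educational workshops". For quantitative items it names rank-sum, chi-squared and binomial tests.

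Before the workshop, Section 13.1.1 provides one instrument. Its timing is given as "Intake will be done upon recruitment, after informed consent is obtained and prior to start the assigned workshop". As to content, the form "gathers information such as demographics, primary care physician (PCP), and insurance coverage". It was not written for this trial: "Forms to be used are the standard intake forms used by MCHH for previous workshop participations". The one survey-type item kept for research asks "What reasons may be stopping you from getting a Pap Test". Section 11 describes the same instrument as "MCHH's standard intake form with an additional question on current barriers to screening".

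After the workshop, Section 13.1.3 defines two surveys, the MCHH-PES and the UW-PSS. On the UW-PSS, Section 13.1.3.2 says "Responses will not be linked to the study ID or other identifiable information". On storage, Section 16.2 says "Post-workshop survey results will be stored in Qualtrics and not linked to study ID, results will be entirely anonymous".

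Section 20.3.1 counts as uptake both screening after the workshop and a stated wish to be screened through a community provider. It also promises uptake by reported ethnicity.

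**The concern.** A pre/post evaluation needs at least one quantity measured on both occasions. Comparing the same woman with herself also needs a link between the two records. The plan appears to supply neither.

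The randomised comparison does not fill the gap. Both arms receive the same core education and differ in the added self-collection component and the screening offer that goes with it. A between-arm difference therefore says nothing about what the core workshop did.

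Two further losses follow from how the survey is stored. Workshops, not women, are randomised, so an analysis of survey answers should be able to tell which workshop each answer came from. And the intention component of uptake is recorded with place of screening in the UW-PSS, which is the unlinked survey.

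**Working it through.** No arithmetic in the plan bears on this point; the power table in Section 20.2 concerns the primary outcome. The check sets the instruments side by side.

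| Instrument | When | Content | Link to the woman |
|---|---|---|---|
| Intake form (13.1.1, Appendix A) | Before | Demographics, last Pap test, insurance, primary doctor, need for help getting a Pap test, barriers checklist | ID number |
| MCHH-PES (13.1.3.1, Appendix A) | After | Four likelihood items | Paper form has an ID number; the Qualtrics copy has none |
| UW-PSS (13.1.3.2, Appendix C) | After | Comfort, preference, future screening, place, concerns | None |

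**Step 1: items asked on both occasions.** None of the intake items asked beforehand reappears afterwards. The four MCHH-PES items are printed on the intake form, but their stem refers to the workshop just attended, so as worded they cannot be asked before it. The nearest candidate is the intake barriers checklist against the question on concerns in Appendix C, Sections C and G. No matching answer list is shown for that question, and it goes only to women not screened at the first offer. The count of common items is 0. The study calendar (Table 2) agrees: it has a row for post-workshop surveys and none for pre-workshop surveys.

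**Step 2: which changes can be estimated.** A paired change needs common items and a link; an aggregate change needs common items only. With 0 common items, neither can be estimated. Lack of common items is the decisive gap. Anonymity is a second obstacle, and it blocks only the paired version and adjustment for linked covariates. With 30 workshops of 8 (Section 11), 30 × 8 = 240 women attend as planned, and 0 of them have a before-and-after pair.

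**Step 3: what remains.** Appendix C asks which type of workshop was attended, so arm is known and post-workshop answers can be compared between arms. The tests named in Section 20.3.2 suit that comparison; none of them is named as a paired test.

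**Step 4: clustering.** Section 11 randomises each workshop as a group, 15 per arm. Appendix C as shown records arm but no session, so the 240 sets of answers can only be treated as independent. With 8 women per workshop the variance inflation is 1 + (8 − 1)ρ = 1 + 7ρ, where ρ is the within-workshop correlation. The documents give no ρ, so I put no size on this.

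**Step 5: the intention component of uptake.** For women not screened at the first offer, Appendix C records intention within a year and intended place, with arm. It can be counted by arm. Appendix C shows no ethnicity or language field, and the data that Section 16.2 places in REDCap include no intention field. The UW-PSS intention component therefore cannot be split by ethnicity as Section 20.3.1 promises.

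**The case against.** The best reply is that this is one loose sentence in a pilot. The secondary objectives in Section 2 are satisfaction and willingness to self-collect. Both need post-workshop answers only, and neither is defined as a change. Section 20.3.2 speaks of qualitative data, names no paired test, and may mean no more than intake barriers reported alongside post-workshop answers. If impact means the effect of the added self-collection education, the randomised comparison delivers it. Anonymity is a deliberate choice, stated twice.

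Much of this stands, and it rules out three stronger readings that a reader might infer.

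- *That there is no pre-workshop questionnaire at all.* There is one, with a barriers item; what it lacks is any item repeated afterwards.
- *That the secondary analysis as a whole fails.* It does not. Satisfaction and willingness can be described, and post-workshop answers compared between arms.
- *That the intention component of the primary outcome cannot be analysed, or exists only in anonymous records.* Arm, same-day screening, intention and place sit in one Qualtrics dataset, so the composite can be counted by arm without an ID. The first MCHH-PES item, on having a Pap or pelvic exam, is also on the ID-numbered paper form held by MCHH. Linking it is physically possible, although the storage plan excludes it and the item does not record place.

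The reply does not rescue the sentence. It promises surveys on both occasions to evaluate the workshops, and the instruments cannot deliver that on a paired or an aggregate basis.

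**Conclusion.** The concern holds in this form. No pre/post change can be estimated: 0 items are common to both occasions and 0 of 240 planned participants have a pair. A between-arm comparison of post-workshop answers is available, but it addresses the added self-collection education. Survey comparisons cannot account for randomisation by workshop, and the UW-PSS intention component cannot be split by ethnicity.

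This rests on Appendix C as shown. The live Qualtrics form may hold fields that the appendix does not print; if it records session or ethnicity, the last two points fall away and the first does not.

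The stakes are moderate. The Section 2 objectives survive, and the arm-level count of uptake is not affected by this point. The plan should still be corrected before workshops run, because baseline answers not collected then cannot be recovered.

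**What to change.** 1. Add a coded workshop ID and a language/ethnicity field to the Qualtrics survey, and account for workshop in the survey comparisons, for example with a random workshop effect or by comparing workshop-level summaries, 15 against 15. Cost: two fields, a wording amendment to Sections 13.1.3.2 and 16.2, and slightly weaker anonymity, since each workshop has only 8 women.

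2. Then choose one of two routes.
   - *Keep the pre/post aim.* Ask the four MCHH-PES likelihood items at intake, with the stem reworded so that it does not refer to a workshop already attended. Link them to the post-workshop answers by a coded ID, and name a paired analysis that accounts for workshop. Cost: four more questions at intake, a further confidentiality amendment, and possibly less candid answers once they are linked. The result would be a before-and-after description of the core workshop, without a randomised control for it.
   - *Keep full anonymity at the level of the woman.* Remove the reference to pre-workshop surveys and restate Section 20.3.2 as post-workshop description and between-arm comparison only. Cost: a text edit, and no statement about the impact of the core education.

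Under either route, state in Section 20.3.1 which record supplies the intention component, so that the ethnicity breakdown can be produced or is withdrawn for that component.
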